## 5 Data handling

### 5.1 General data handling information

Data collection, handling, processing and transfer for the purpose of this Study will be performed in compliance with applicable regulations, guidelines for clinical studies and internal procedures. It remains the responsibility of the Investigator to check that all data relating to the Study, as specified in the Study protocol, are entered into the electronic Case Report Form ((e)CRF) in accordance with the instructions provided and that the forms are filled out accurately, completely and in a timely manner.

(e)CRFs are provided by the Sponsor for each participant. The Study data will be transcribed from the source records into an (e)CRF by Study Staff.

The (e)CRFs shall under no circumstances capture personal data such as but not limited to the participant or their relative(s) name, home address, contact details, full date of birth medical record number (e.g. UZ Leuven EAD number), social security number etc.

Transfer of the pseudonymized data will be performed via a secured method of transfer taking into account all applicable security arrangements and regulations (such as the European General Data Protection Regulation). The receiving party will be bound by contractual agreement to keep the transferred data confidential at all times and to only process the data for the purpose of the Study. To this end, appropriate Data Transfer Agreements (DTAs) will be established.

### 5.2 Study specific data handling information

The data will be stored in a secure RedCap database on the UZ Leuven, and will only be accessible to specific persons: [name]. [name], the CTA [name] and possible monitors from the CTC, if required. Data will be stored for a period of 20 years.

[KWS] will be used to capture study related data.

The following data will be collected in the (e)CRF :

**Primary endpoint: Study product efficacy (success, defined as follows):**

From the surgical report, the following data will be extracted:

1. In case of surgery for macular hole or vitreomacular traction:

- A. Was the staining of the ILM satisfactory to initiate the peeling: yes / no
- B. Was the staining of the ILM satisfactory to create the ILM rhexis: yes / no
- C. Was it necessary to use another vital dye in order to obtain satisfactory staining: yes / no

Success is defined as answer “yes” to 1.A and/or 1.B

2. In case of surgery for macular pucker:

- A. Was the staining of the ERM satisfactory for its removal: yes / no
- B. In case the ILM was removed separately from the ERM:
  - i. Was the staining of the ILM satisfactory to initiate the peeling: yes / no
  - ii. Was the staining of the ILM satisfactory to create the ILM rhexis: yes / no
- C. Was MONOBLUE DUAL View repeatedly injected: yes / no
- D. Was it necessary to use another vital dye in order to remove the ERM: yes / no
- E. Was it necessary to use another vital dye in order to remove the ILM: yes / no

Success is defined as “yes” answer to 2.A and 2B.i or 2B.ii

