A few years later, Brilliant Blue G (BBG) was commercialized to selectively stain ILM, and is today still the golden standard for ILM staining. BBG offers a good and selective staining of the ILM, and is a rather transparent solution, hence the surgeon can see the surface of the retina during the surgery. However, BBG hardly stains the ERM.

The first commercial TB and BBG vital dyes were dissolved in BSS, hence had the same gravity as the BSS used to infuse the eye during vitrectomy surgery. As a result, when injecting a 'cloud' of the vital dye, it was difficult for the dye to reach and color specifically the desired retinal tissue. In newer commercial products, the dyes are dissolved in a heavier-than-water dissolvent (such as poly-ethylene glycol: PEG), which makes them sink down to the retinal surface when injected in the vitreous cavity during surgery.

Since it is frequently necessary to remove both ILM and ERM during vitrectomy surgery, solutions that combine TB and BBG are now also available.

In UZLeuven, two types of vital stains are being used during vitrectomy surgery:

- BBG 0,025 % dissolved in PEG (ILM Blue® – DORC): when only ILM peeling is required.
- BBG 0,025 % + TB 0.15% dissolved in PEG (Membrane Blue Dual® – DORC): when either ERM removal is required, or combination of ERM + ILM removal.

More recently, two new staining dyes were commercialized by ARCADOPHTA:

- Monoblue ILM View: DDG 0.025 % dissolved in PBS (phosphate buffer saline) with 2.6% diglycerol. DDG is a triphenylmethane dye with a chemical formula:  $C_{46}H_{46}N_3NaO_7S_2$  and a molecular weight of 840 Dalton. This dye is used to stain the ILM, similar as ILM Blue. The diglycerol makes it heavier than water to optimize the contact between the dye and the retina, similar as ILM Blue.
- Monoblue Dual View: DDG 0.025 % and Trypan Blue 0.09% dissolved in PBS with 2.6% diglycerol, which is used the same way as Membrane Blue Dual.

In laboratory and ex vivo tests, it was shown that both dyes have the following properties:

- Monoblue ILM view:
  - It stains ILM as good as ILM Blue.
  - It is heavier than water, hence sinks down to the retinal surface.

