## 4 Statistics and Data Analysis

The primary outcome of the study is the success of the products based on assessment of efficacy of the staining dye.

Safety of the dye will be assessed by comparing the surgical outcome of the patients to a similar control group that underwent surgery using the staining dyes presently used in our department (see study endpoints).

Statistical analyses will be performed with R version 3.6.2 or higher. In case of missing values, the underlying missingness process (MCAR, MAR or MNAR) will be investigated and 15 multiple imputations will be performed using the **MICE** R package.

We will test with the statistical test of Jamshidian and Jalal (2010), implemented in the **MissMech** R Package (Jamshidian, Jalal & Jansen, 2014), whether missing data were MCAR. If they were not MCAR, we investigated whether or not the missing mechanism could be explained by baseline characteristics (eg, sociodemographic, medical features) of patients using logistic regression, which would suggest an MAR mechanism. If missing data were not MCAR or MAR, they were considered as MNAR.

For each dataset created, two propensity scores will be performed: a first one between the Monoblue ILM View and the ILM Blue, and a second one between the Monoblue Dual View and Membrane Blue Dual. The next covariates were selected for the propensity score: age, gender, visual acuity of the affected eye, surgery type of the affected eye (vitrectomy only vs phaco and vitrectomy). The Covariate Balancing Propensity Score provided in the R **CBPS** package (Imai & Ratkovic, 2014) will be used to estimate an Average Treatment Effect (ATE). The ATE will be estimated by covariate balancing and requesting an exact match. An absolute standardized difference less than 10–15% will be considered to support the assumption of balance between the groups. Unlike the P-value, this method is not affected by the sample size, and it could be used to compare the relative balance of variables that were measured in different units (Austin, 2011). Results (obtained after matching) will be expressed as the mean and standard deviation (SD) for continuous variables or the percentage for categorical variables. The **survey** R package will be used to perform linear regressions for continuous outcome variables and logistic regressions for binary variable. These regressions

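### Success items follow diagnosis but the comparison follows dye, so a dual-dye eye with a hole or traction plus an epiretinal membrane can count as a success without any ERM assessment

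*Combined protocol and SAP*

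**What the plan says.** **Choice of items (section 5.2, primary endpoint).** List 1 applies "In case of surgery for macular hole or vitreomacular traction". Its success items, 1.A and 1.B, both concern the ILM. The first reads "Was the staining of the ILM satisfactory to initiate the peeling: yes / no", and a yes to either is enough. Item 1.C, "Was it necessary to use another vital dye in order to obtain satisfactory staining: yes / no", names no membrane and is not part of success. List 2 applies "In case of surgery for macular pucker". Only there does the ERM item 2.A appear: "Was the staining of the ERM satisfactory for its removal: yes / no".

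**Unit of comparison (section 4).** Two propensity scores are planned, one for the ILM dyes and "a second one between the Monoblue Dual View and Membrane Blue Dual". The covariates are age, gender, visual acuity and surgery type. Neither diagnosis nor presence of an ERM is among them.

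**Choice of dye (section 1, Background and Rationale).** The reference dual dye is used "when either ERM removal is required, or combination of ERM + ILM removal", and Monoblue Dual View is described as used in the same way.

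**Eligibility (sections 3.1 and 3.2).** Eyes needing removal of the ILM, the ERM or both are admitted. Hole and traction are annotated as ILM staining, and pucker as ILM and ERM staining. A hole or traction eye that also needs ERM removal is not excluded.

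**The concern.** Three classifications are in play: diagnosis selects the questions, the membrane to be removed selects the dye, and the dye selects the comparison. They agree when every hole or traction eye needs only ILM peeling. They part when such an eye also has an ERM to remove. That eye receives a dual dye and enters the dual-dye comparison, yet its diagnosis leads to a list with no ERM question.

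ERM staining is the open question for Monoblue Dual View. It contains 0.09% trypan blue against 0.15% in the comparator, and the Background only expects equal ERM staining. The hypothesis in section 2.3 is non-inferiority, so anything that pulls the two success rates together favours the study product. Section 2.1 says the results may be used to decide whether to replace the hospital's standard dyes. The controls come from three earlier studies, so an equal case mix in the two arms cannot be taken for granted.

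**Working it through.** The plan gives no sample size, margin, expected success rate or count of mixed eyes, so there is no figure to reproduce. All rates below are assumptions.

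**Set-up.** Let p be the probability that ERM staining is satisfactory, q the probability of success on the ILM items, and f the share of dual-dye eyes scored by list 1. Assume every dual-dye eye has an ERM removed and its ILM peeled separately, the items are independent, and list 2 success means 2.A together with at least one of 2.B.i and 2.B.ii. Then:

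- success rate in an arm: s = (1 − f)·p·q + f·q
- difference between arms, with q and f equal in both: d = (1 − f)·q·(p_control − p_study)

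The observed difference is the true one multiplied by (1 − f).

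**Setting A.** Each ILM item is satisfactory in 95% of eyes, so q = 1 − 0.05² = 0.9975. ERM staining is 95% (control) against 80% (study). True difference: 0.9975 × 0.15 = 0.1496, or 15.0 points.

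**Setting B.** q = 0.98, ERM staining 95% against 85%. True difference: 0.98 × 0.10 = 0.098, or 9.8 points. With an assumed 10-point margin, n = 100 per arm and one-sided 0.025, P(declare non-inferiority) = Φ((0.10 − d)/SE − 1.96), where SE = √[(s_C(1 − s_C) + s_S(1 − s_S))/n].

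| f | A: observed deficit (points) | B: observed deficit (points) | B: P(declare non-inferiority) |
|---|---|---|---|
| 0 | 15.0 | 9.8 | 2.8% |
| 5% | 14.2 | 9.3 | 3.6% |
| 10% | 13.5 | 8.8 | 4.6% |
| 20% | 12.0 | 7.8 | 7.5% |
| 30% | 10.5 | 6.9 | 12.0% |

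Example for B at f = 30%: s_C = 0.9457, s_S = 0.8771, d = 0.0686, SE = √[(0.9457 × 0.0543 + 0.8771 × 0.1229)/100] = 0.0399, and Φ(0.0314/0.0399 − 1.96) = 0.120.

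Setting B puts the true deficit just inside the margin, where the probability is sensitive to dilution. With ERM staining at 80% in the study arm and q = 0.98, the true deficit is 14.7 points, well beyond the margin. The probability then rises only from 0.2% at f = 0 to 2.1% at f = 30%.

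**Unequal f.** With equally good dyes, the difference between arms is q·(1 − p)·(f₁ − f₂). With q = 0.9975, p = 0.90 and shares of 30% and 10%, it is 0.9975 × 0.10 × 0.20 = 0.020. The arm with more list 1 eyes appears 2.0 points better, whichever arm that is.

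**The case against.** The strongest reply is that the problem may hardly occur. Section 3.1 pairs hole and traction with ILM staining and pucker with both membranes, so on the protocol's own mapping diagnosis, membrane and dye coincide. No count of mixed eyes is given. At f = 5% the assumed 15-point deficit falls only to 14.2. This stands as a limit on size. It does not remove the gap, because the eligibility criteria admit such eyes.

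A reader might infer that these eyes are never asked about the ERM. The documents do not settle that. The Background describes pucker as fibrosis over the macula, and section 5.2 does not make the lists mutually exclusive, so an extractor could treat the surgery as pucker surgery too and apply item 2.A. What stands is that the choice is left undefined for a primary endpoint.

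A reader might also infer that the endpoint hides failures of the dye with less trypan blue in particular. The same list applies to both dual dyes, and item 1.C could record that a second dye was needed. But 1.C does not enter success, and a real difference between the dyes would still be diluted.

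Finally, the mismatch might seem to run the other way as well, with pucker eyes given an ILM-only dye and judged on ERM staining, given the Background's remark on the reference ILM dye: "However, BBG hardly stains the ERM". The documents do not support this. The Background reserves ILM Blue for ILM-only peeling, and the Intended Use limits Monoblue ILM View to the ILM.

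**Conclusion.** The concern holds as a gap in the endpoint rule. Read literally, section 5.2 lets a hole or traction eye with an ERM count as a success in the dual-dye comparison with no ERM assessment, and the plan has no rule for mixed diagnoses. With equal shares in both arms, this shrinks any true ERM-staining difference by (1 − f), in the direction that favours non-inferiority. With unequal shares the bias can go either way, and the planned propensity covariates do not target it.

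The size is unknown because f is unknown. The effect is small at 5% and material at 20% to 30%, shares for which the documents offer no evidence. The figures also rest on the assumed staining rates, independence of items, separate ILM peeling in every dual-dye eye, and the stated reading of list 2 success. The documents do not show that ERM failures are in fact being hidden.

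**What to change.** In section 5.2, choose the items by membrane removed, whatever the diagnosis:

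- Ask item 2.A in every eye in which an ERM was removed.
- Ask the ILM items in every eye in which the ILM was peeled separately.
- Define success in the dual-dye comparison on the membranes actually removed.
- Report the mix of diagnoses and membranes removed by arm, so that a reader can see f and any imbalance.

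This rewords one list before extraction and uses the same surgical reports. Eyes stay in the comparison set by their dye. The cost is that some control reports, written for earlier studies, may not rate ERM staining in hole or traction eyes. Those items would be missing and would fall under the multiple imputation in section 4, so their number should be reported by arm.

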### 2.3 Secondary Endpoints

- Efficacy: subjective assessment of surgical help provided by the product
- Safety:
  - Rate and severity of potential study-related products adverse events
  - Visual outcome at the last postoperative visit

The study hypothesis to be verified is non-inferiority in term of efficacy between study products and comparator based on a binary subjective evaluation of visualization of membranes stained. The proportion of success between study products and comparator will be studied, covariates (age, gender, visual acuity in the affected eye, surgery type being vitrectomy or phaco plus vitrectomy) taken into using a propensity score methodology.

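### The success rules in section 5.2 leave out the recorded need for another dye, so an eye with one satisfactory step that then needed a second dye counts as a success

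*Combined protocol and SAP*

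**What the plan says.** Section 5.2 lists yes/no items to be extracted from the surgical report, under the heading "Primary endpoint: Study product efficacy (success, defined as follows".

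- Macular hole and vitreomacular traction: 1.A is "Was the staining of the ILM satisfactory to initiate the peeling: yes / no", 1.B asks the same about creating the rhexis, and 1.C is "Was it necessary to use another vital dye in order to obtain satisfactory staining: yes / no". The rule is "Success is defined as answer “yes” to 1.A and/or 1.B".
- Macular pucker: 2.A concerns ERM staining. 2B.i and 2B.ii concern ILM staining where the ILM was removed separately. 2.C concerns repeat injection, 2.D is "Was it necessary to use another vital dye in order to remove the ERM: yes / no" and 2.E is "Was it necessary to use another vital dye in order to remove the ILM: yes / no". The rule is "Success is defined as “yes” answer to 2.A and 2B.i or 2B.ii".

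Items 1.C, 2.D and 2.E appear in neither rule, and nothing elsewhere brings them in. Section 2.2 refers the reader to study endpoints in section 3, which holds only eligibility criteria. Section 4 adds no detail to the definition and plans no analysis of the switch items. The secondary endpoint on surgical help (section 2.3) is not linked to them. Section 2.3 states the hypothesis as "non-inferiority in term of efficacy between study products and comparator based on a binary subjective evaluation of visualization of membranes stained".

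**The concern.** A yes to 1.C is the protocol's own record that the first dye did not, in the end, stain well enough. The rule can nevertheless credit that eye to the first dye, because one satisfactory step is sufficient. The eyes affected are those in which the first dye worked for one step and not for a later one. That kind of failure could separate two similar dyes.

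The success proportion carries the non-inferiority hypothesis, and section 2.1 says the results may be used to decide whether the study dyes replace the hospital's current ones. Scoring partial failures as successes moves both arms towards 100% and shrinks any difference that arises from them. If the study dye needs rescue more often, this favours a non-inferiority finding. If the comparator does, it hides an advantage of the study dye.

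**Working it through.** The plan gives no sample size, margin, expected success rate or rescue rate, so there is no figure of its own to reproduce. The check has two parts: which answer patterns the printed rules accept, and how far the difference could move.

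**Hole and traction.** Three yes/no items give 2 × 2 × 2 = 8 patterns. The rule accepts 3 of the 4 combinations of A and B, with either answer to C: 3 × 2 = 6 successes, of which 3 have 1.C = yes. Now take the reading kindest to the plan: A and B describe the first dye only, and another dye is needed only if A or B is no. This removes yes/yes/yes. Two accepted patterns with a switch remain:

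- 1.A = yes, 1.B = no, 1.C = yes
- 1.A = no, 1.B = yes, 1.C = yes

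Requiring 1.C = no leaves 3 successes of 8.

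**Pucker, ILM removed separately.** Six items give 64 patterns. The rule has no brackets, so both readings were run. The kind reading here is that 2.D = yes implies 2.A = no, and 2.E = yes implies that 2B.i or 2B.ii is no.

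| Reading | Successes | With 2.D or 2.E = yes | Still with a switch on the kind reading | Successes if 2.D = 2.E = no |
|---|---|---|---|---|
| 2.A and (2B.i or 2B.ii) | 3 × 8 = 24 | 18 | 4 | 3 × 2 = 6 |
| (2.A and 2B.i) or 2B.ii | 5 × 8 = 40 | 30 | 12 | 5 × 2 = 10 |

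An example that passes under both readings is 2.A = yes, 2B.i = yes, 2B.ii = no, 2.E = yes. Under the second reading, an eye with 2.A = no and 2.D = yes also passes if 2B.ii = yes. These are counts of answer patterns, not patient rates.

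**Size, on assumed rates.** Let r be the share of eyes needing another dye, and k the share of those eyes that still meet the printed rule; T is the study dye and C the control. Counting a switch as failure lowers success in each arm by k × r, so the difference T − C shifts by −(k_T × r_T − k_C × r_C). With a common k this is −k × (r_T − r_C), largest in size at k = 1. Assume that no eye fails for any other reason:

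| r_T, r_C | k | Printed rule, T vs C | Switch = failure, T vs C | Shift (points) |
|---|---|---|---|---|
| 2%, 2% | 1 | 100% vs 100% | 98% vs 98% | 0 |
| 10%, 2% | 1 | 100% vs 100% (0) | 90% vs 98% (−8) | −8 |
| 15%, 2% | 1 | 100% vs 100% (0) | 85% vs 98% (−13) | −13 |
| 10%, 2% | 0.5 | 95% vs 99% (−4) | 90% vs 98% (−8) | −4 |
| 10%, 2% | 0 | 90% vs 98% (−8) | 90% vs 98% (−8) | 0 |
| 2%, 10% | 1 | 100% vs 100% (0) | 98% vs 90% (+8) | +8 |

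The difference in rescue rates is thus an upper bound when k is the same in both arms. If k differs between arms, the bound is the larger of the two rescue rates.

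**The case against.** The strongest reply is that the items sit under a heading about the study product and ask separately about another dye, so A and B naturally refer to the first dye. A dye that failed outright (A = no, B = no) is then already a failure. This stands. A reader might infer that the rule credits a dye that failed completely with the result of the second dye. The wording leaves that possible, since A and B do not name the dye, but nothing in the documents shows that answers would be extracted that way. What the text does establish is the narrower case of partial failure, which survives the kind reading.

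Second, requiring 2.D = no looks redundant: if 2.A refers to the first dye, 2.D = yes means 2.A = no. That is right under 2.A and (2B.i or 2B.ii), but not under the other bracketing.

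Third, the objectives do not say that the dye must succeed alone; section 2.1 speaks of adequate aid to the surgeon. Whether a stain that let the peel start is a success is partly the sponsor's choice. That is a reason to keep the present definition as a supportive analysis. It does not explain why items collected on exactly this question have no role in the plan.

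Fourth, the controls come from three earlier studies (S61408, S63610, S64913; section 2.1), and the documents do not say whether dye switching was recorded there. Item 2.C names only the study product. If control reports mention switching less reliably, a stricter rule could lower success mainly in the study arm, or send control values to the multiple imputation of section 4. This stands, and it conditions the fix.

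**Conclusion.** The point holds as a defect in the definition: both success rules accept eyes in which another dye was recorded as necessary, even when A and B are read as describing the first dye only. The effect is to hide partial failures.

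Its size cannot be determined from the documents. The figures of 8 and 13 points rest on assumed rescue rates, on every rescued eye meeting the printed rule, and on no other failures. No margin is stated against which to judge them. A reader might also infer a bias in favour of the study dyes. The documents do not support that: the rule applies to both arms, and the direction depends on which arm needs rescue more often.

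The change is still worth making before outcomes are compared, because a choice between the two definitions would not be credible afterwards.

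**What to change.** In section 5.2:

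- State that A and B are answered for the first dye injected, before any other dye is used.
- For hole and traction, success also requires 1.C = no. For pucker, it also requires 2.D = no and 2.E = no (or not applicable).
- Analyse each eye under its first dye.
- Keep the current definition as a supportive analysis.

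The missing brackets in the pucker rule, and the outcome for eyes whose ILM was not removed separately, are separate matters best settled in the same edit.

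Before adopting the rule, confirm that dye switching can be extracted from the control surgical reports as completely as from the study-dye reports. If it cannot, report the no-switch version as a prespecified sensitivity analysis instead.

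A safety comparison that leaves out eyes given two dyes is best avoided, or labelled exploratory: it selects on a post-treatment event, and rescued eyes may be the harder ones.

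The cost is a wording change, a check of the control reports, and possibly slightly lower success rates. The items are already listed for the eCRF, and no clinical care changes.

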#### Monoblue Dual View

- Monoblue Dual View may offer better transparency to see the retinal surface during surgery compared to Membrane Blue Dual.
- It has a lower concentration of TB, but is still expected to stain ERM as effectively as Membrane Blue Dual, but with a potential better safety profile since its lower concentration.

Both above mentioned dye solutions were CE marked on April 22, 2021 by ARCADOPHTA, located [name], known as the legal manufacturer (see to CE certificate and Declaration of Conformity (DC) provided herewith in **Appendix IA, IB, IC**).

We obtained approval from the CMM UZLeuven to perform a demo with these products. For this purpose, samples of Monoblue ILM View and Monoblue Dual View were obtained from the manufacturer.

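### The pucker success rule lacks brackets and a branch for eyes without separate ILM removal, and the hole/traction rule passes an eye on one of two steps

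*Combined protocol and SAP*

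**What the plan says.** Primary success is defined in one place, the primary-endpoint block of section 5.2. Section 2.2 points to section 3 for the definition, but section 3 contains eligibility only.

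- **Macular hole and vitreomacular traction.** Two ILM items are recorded: 1.A, "Was the staining of the ILM satisfactory to initiate the peeling: yes / no", and 1.B, "Was the staining of the ILM satisfactory to create the ILM rhexis: yes / no". The rule is "Success is defined as answer “yes” to 1.A and/or 1.B".
- **Macular pucker.** Item 2.A asks "Was the staining of the ERM satisfactory for its removal: yes / no". The two ILM items, 2B.i and 2B.ii, sit under a condition: "In case the ILM was removed separately from the ERM". The rule is "Success is defined as “yes” answer to 2.A and 2B.i or 2B.ii". It has no brackets and does not mention the case in which 2.B was not answered.

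Section 2.3 frames the hypothesis as non-inferiority on the proportion of success and gives no margin. Section 4 plans weighted logistic regression for binary outcomes and multiple imputation for missing values. No expected success rate or sample size is stated.

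**The concern.** The pucker sentence can be programmed in two ways, so the same data can yield two primary results. The two codings differ on eyes where ERM staining was unsatisfactory but ILM staining for the rhexis was satisfactory. That pattern matters for this comparison. Section 1 gives trypan blue as 0.09% in Monoblue Dual View and 0.15% in Membrane Blue Dual, and says of the former: "It has a lower concentration of TB, but is still expected to stain ERM as effectively as Membrane Blue Dual". ERM staining is the property this endpoint needs to test.

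The conditional item 2.B adds a second gap. If the ILM came away with the ERM, 2.B is blank, and the rule does not say whether such an eye can succeed. A blank could be coded as a failure or passed to the imputation model, although nothing is missing.

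The hole/traction rule is clear but lenient. The protocol asks about two steps and then lets a yes on one override a no on the other, without giving a reason. In a non-inferiority comparison of proportions, a rule that narrows the difference favours the study product.

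**Working it through.** The plan states no rate, margin or sample size, so there is no figure of its own to reproduce. Every rate below is an assumption.

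**Pucker rule: answer patterns.** Items 2.A, 2B.i and 2B.ii give 8 yes/no patterns.

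| 2.A, 2B.i, 2B.ii | (2.A and 2B.i) or 2B.ii | 2.A and (2B.i or 2B.ii) | all three |
|---|---|---|---|
| yes, yes, yes | pass | pass | pass |
| yes, yes, no | pass | pass | fail |
| yes, no, yes | pass | pass | fail |
| yes, no, no | fail | fail | fail |
| no, yes, yes | **pass** | fail | fail |
| no, yes, no | fail | fail | fail |
| no, no, yes | **pass** | fail | fail |
| no, no, no | fail | fail | fail |

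The first reading passes 5 patterns and the second 3. The two extra passes are exactly those with 2.A = no and 2B.ii = yes.

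**Pucker rule: size.** Assume ERM success a = 0.95 (control) and 0.85 (study), and each ILM step b = 0.90 in both arms, all independent.

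- First reading, b + (1 − b)·a·b: 0.90 + 0.10 × 0.95 × 0.90 = 0.9855; 0.90 + 0.10 × 0.85 × 0.90 = 0.9765. Difference 0.9 points.
- Second reading, a·[1 − (1 − b)²]: 0.95 × 0.99 = 0.9405; 0.85 × 0.99 = 0.8415. Difference 9.9 points.
- If the two ILM answers always agree, the first reading reduces to the ILM answer alone: 0.90 in both arms, difference 0. The second gives 0.95 × 0.90 = 0.855 and 0.85 × 0.90 = 0.765, difference 9.0 points.

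**Pucker rule: blank 2.B.** If a blank is scored as no, an eye with 2.A = yes and 2.B blank fails under the second reading, and also under the first. If 20% of pucker eyes are of this kind (assumed), success cannot exceed 80% however good the dye.

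**Hole/traction rule.** Of 4 patterns, the either-step rule passes 3 and a both-steps rule passes 1. Let p be the success probability of each step and ρ the within-eye correlation of the two answers:

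- P(both) = p² + ρ·p(1 − p)
- P(either) = 2p − P(both)

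With p = 0.95 (control) and 0.85 (study):

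| ρ | Either step | Difference | Both steps | Difference |
|---|---|---|---|---|
| 0 | 99.75% vs 97.75% | 2.0 | 90.25% vs 72.25% | 18.0 |
| 0.6 | 96.9% vs 90.1% | 6.8 | 93.1% vs 79.9% | 13.2 |
| 1 | 95% vs 85% | 10.0 | 95% vs 85% | 10.0 |

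**When the narrowing holds.** Under these formulas the either-step difference is the smaller one only when mean step success exceeds 50% and ρ is below 1. Below 50% it reverses: at 40% versus 30% with ρ = 0, either-step gives 0.64 − 0.51 = 13 points and both-steps gives 0.16 − 0.09 = 7 points.

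**Odds-ratio scale.** At ρ = 0 and 95% versus 85%, the either-step odds ratio is (0.9975/0.0025)/(0.9775/0.0225) = 9.18. The both-steps odds ratio is (0.9025/0.0975)/(0.7225/0.2775) = 3.56. At ρ = 0.6 they are 3.43 and 3.39. The odds ratio does not narrow under the either-step rule here, although at ρ = 0 very few failures remain to estimate it.

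**The case against.** **The layout points to one pucker reading.** Items i and ii are sub-items of B, and the hole/traction rule joins the same two ILM steps with an inclusive or. A clinician would probably mean 2.A and (2B.i or 2B.ii), under which failed ERM staining never passes. This stands. A reader might infer that the plan scores ERM failures as successes; the documents support only that one possible coding would do so. The favoured reading still leaves blank 2.B unresolved.

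**The either-step rule is explicit and applies equally to all dyes.** Nowhere do the documents say that a dye must serve both steps, and section 2.1 speaks of adequate aid in visualisation. This also stands. Calling the rule an error would go too far; what is missing is its justification.

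**The narrowing depends on scale and correlation.** A reader might infer that real differences always shrink. They need not on the odds scale of the planned model. The 2-versus-18 contrast also needs independent answers, which is unlikely for one dye on one membrane in one eye. The point survives for the difference in proportions, the scale on which section 2.3 frames the hypothesis.

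**A both-steps rule needs more data.** One yes settles the either-step rule, whereas a both-steps success needs two recorded answers. Controls come from three earlier studies of gauge or equipment, so missing answers may increase there. This is a real cost.

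**Conclusion.** The concern holds in two parts of unequal strength.

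1. The pucker rule needs correcting on its text alone. It has two codings, one of which passes eyes with failed ERM staining, and it gives no result for eyes with 2.B blank. Under the rates assumed above, the choice of coding moves the difference between dyes from 0.9 to 9.9 points.
2. The hole/traction rule is clear but unjustified. Where step success is high and the two answers are imperfectly correlated, it narrows the difference in proportions: 2 to 10 points against 10 to 18, at assumed step success of 95% versus 85%, with ρ from 1 down to 0 taken the same in both arms.

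Without a stated margin or sample size, no effect on the non-inferiority decision itself can be shown. Replacing the either-step rule outright is partly a design preference.

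**What to change.** Before data extraction or analysis, amend section 5.2:

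- **Pucker:** success = 2.A yes AND, where the ILM was removed separately, the ILM criterion met. Otherwise 2.B is not applicable, and is neither scored as no nor imputed.
- **Both-steps analysis:** prespecify 1.A AND 1.B, and 2.A AND 2B.i AND 2B.ii where applicable, beside the either-step rule. Make it primary if the sponsor cannot justify one satisfactory step as sufficient.
- **Related gap, same edit:** state how use of another dye is scored. For example, 1.C, "Was it necessary to use another vital dye in order to obtain satisfactory staining: yes / no", is collected, as are 2.D and 2.E, but none of them enters success.

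The cost is a wording change and one further analysis of items already on the case report form. The both-steps rule will give lower success rates in both groups. It may also leave more outcomes missing because both answers must be recorded, particularly in the controls taken from earlier studies.
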